8.5 Guidelines for Evaluation of Measurable Disease

Measurable extra nodal disease should be assessed in a manner similar to that for nodal disease. For these recommendations, the spleen is considered nodal disease. Disease that is not easily assessable (e.g., pleural effusions, bone lesions) will be recorded as present or absent only, unless, while an abnormality is still noted by imaging studies it is found to be histologically negative.

Clinical lesions will only be considered measurable when they are superficial (e.g., skin nodules, palpable lymph nodes).

Lesions on chest X-ray are acceptable as measurable lesions when they are clearly defined and surrounded by aerated lung. However, CT or PET/CT is preferable.

Conventional CT and MRI should be performed with cuts of 10 mm or less in slice thickness contiguously. Spiral CT should be performed using a 5 mm contiguous reconstruction algorithm. This applies to the chest, abdomen, and pelvis. Head & neck and extremities usually require specific protocols.

Ultrasound should not be used to measure tumor lesions that are clinically not easily accessible when the efficacy endpoints of the study is objective response evaluation. It is a possible alternative to clinical measurements of superficial palpable nodes, subcutaneous lesions, and thyroid nodules. Ultrasound might also be useful to confirm the complete disappearance of superficial lesions usually assessed by clinical examination.

8.6 Particular Case of Waldenstrom Macroglobulinemia

Table 4

Categorical Response Definitions	
Response category	Definition
Complete response (CR)	Absence of serum monoclonal IgM protein by immunofixation Normal serum IgM level Complete resolution of extramedullary disease, i.e., lymphadenopathy and splenomegaly if present at baseline Morphologically normal bone marrow aspirate and trephine biopsy
Very good partial response (VGPR)	Monoclonal IgM protein is detectable ≥90% reduction in serum IgM level from baseline* Complete resolution of extramedullary disease, i.e., lymphadenopathy/splenomegaly if present at baseline No new signs or symptoms of active disease
Partial response (PR)	Monoclonal IgM protein is detectable ≥50% but <90% reduction in serum IgM level from baseline* Reduction in extramedullary disease, i.e., lymphadenopathy/splenomegaly if present at baseline No new signs or symptoms of active disease
Minor response (MR)	Monoclonal IgM protein is detectable ≥25% but <50% reduction in serum IgM level from baseline* No new signs or symptoms of active disease

Categorical Response Definitions	
Response category	Definition
Stable disease (SD)	
Monoclonal IgM protein is detectable <25% reduction and <25% increase in serum IgM level from baseline*
 
No progression in extramedullary disease, i.e., lymphadenopathy/splenomegaly
 
No new signs or symptoms of active disease

Progressive disease (PD)	
≥25% increase in serum IgM level* from lowest nadir (requires confirmation) and/or progression in clinical features attributable the disease

* Sequential changes in IgM levels may be determined either by M protein quantitation by densitometry or total serum IgM quantitation by nephelometry
 For more details, please refer to <http://www.ncbi.nlm.nih.gov/pubmed/23150997>¹⁴

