3. PATIENT SELECTION

3.1. Eligibility Criteria

3.1.1. Inclusion Criteria (must meet all)

1. Histologically documented (by HPI or pathology report) iNHL as defined by follicular lymphoma (FL), marginal zone lymphoma (MZL), lymphoplasmacytic lymphoma/Waldenstrom disease (LPL/WM) and small lymphocytic lymphoma (SLL) or tiNHL as defined by large B cell transformation of any of the above entities including chronic lymphocytic leukemia (CLL)
2. Patients must be eligible to undergo high dose chemotherapy (HDT) followed by ASCT as a form of remission consolidation
3. Patients without evidence of documented disease progression clinically or radiographically after ASCT (stable disease (SD), partial remission (PR) or complete remission (CR)) who have had count recovery (ANC > 500 cells/mm³, non-transfused platelet count > 20,000 K/mm³) and are at least 30 days post ASCT but no more than 120 days post ASCT

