6. REQUIRED DATA/STUDY CALENDAR

Pre-Study Testing Intervals

To be completed within 16 DAYS before study treatment:

- All blood work
- History and physical

To be completed within 28 DAYS before study treatment:

- Any X-ray, scan of any type (e.g., CT or MRI) or ultrasound that is utilized for tumor measurement

To be completed within 42 DAYS before study treatment:

- Any X-ray, scan of any type (e.g., CT or MRI) or ultrasound that is not utilized for tumor measurement
- Bone marrow biopsy and aspirate (unilateral) is required if there washistory of bone marrow involvement.

	Prior to Treatment	Cycle 1 Day 1	Cycle 1 Day 8 ± 3 days	Cycle 1 Day 15 ± 3 days	Day 1 of Each Subsequent Cycle ± 3 days ^l	Cycle 2 Day 15 ± 3 days	Cycle 3 Day 15 ± 3 days	End of Treatment* * ± 3 days	Time of Restaging and Post-treatment Follow-up*, %
Tests & Observations									
History & Progress Note	X	X			X			X	X
Physical Examination	X	X			X			X	X ^j
Pulse, Blood Pressure	X	X			X			X	X
Height	X								
Weight	X	X			X			X	X
Performance Status	X	X			X			X	X
Drug Toxicity Assessment	X	X			X			X	
Solicited Abnormalities/AEs	X	X ^A			X ^A			X	
Laboratory Studies									
CBC, Diff, Platelets	X	X			X			X	X
Serum Creatinine, CrCl (est), BUN	X	X			X			X	X
Serum Electrolytes	X	X			X			X	X
AST, ALT, Alk Phos, Bilirubin	X	X		X	X ^A	X	X	X	X
Uric Acid, Phosphate, LDH	X	X			X			X	X
Blood CMV PCR	X	X			X			X	
Beta2-Microglobulin	X							X	

Serum or Urine BHCg	X ^B							X	
Thyroid Function Tests (T3,T4, TSH)	X ^E				X ^E			X	
Triglycerides	X ^I							X	
HIV~	X ^{C~}							X	
HBsAg~, Anti-HBc~Ab,HepC Ab~	X~							X	
ECG	X		X ^F					X	
Staging									
CT/MRI (chest/abd/pelvis) with Tumor Measurements	X							X	X ^D
CT Neck	X							X	X ^D
PET (or PET/CT)	X							X	X ^D
Bone Marrow Asp & Biopsy	X							X ^G	X ^G
Histologic Review	X							X ^K	
Correlative Samples	X ^H	X ^H						X ^H	X ^H

Table 1

* Restage every 3 cycles during treatment (i.e., cycles 3, 6, 9, 12, etc.), then every 3 months for 1 year, then every 6 months for another year.

** If off study prior to month 12 study treatment

% Starting at cycle 15 through cycle 24: Visit window +/- 4 weeks. Starting at cycle 27 through cycle 36: Visit window +/- 12 weeks.

^ Monitor ALT, AST, Alk Phos and bilirubin in all patients every 2 weeks (or 15 days) for the first 3 cycles of treatment, than every 4 weeks during subsequent cycles.

~ If done before the transplant, no need to repeat them.

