A. Abnormalities/adverse events should be solicited, and severity graded, on day 1 of each cycle of treatment.

B. In women of childbearing potential (as defined in Section 3.1.7). A negative serum or urine HCG test is required within 14 days prior to study.

C. Patients with known HIV positivity are excluded.

D. CT, PET or PET/CT done PRN to follow measurable disease. Scan to be done with or without PET depending on the patient disease status.

- E. Thyroid function tests every 3 cycles while on treatment and at completion of protocol therapy(Prior to treatment, C3D1, C6D1, C9D1, C12D1).
- F. ECG on day 8 of cycle 1, and then as clinically indicated. The steady-state (day 8) ECG is a requirement of the FDA under the Alliance IND for Zydelig.
- G. Repeat bone marrow aspirate and biopsy to confirm CR only if involved at baseline. Also a bone marrow aspirate/biopsy will be done if suspicion of bone marrow involvement.
- H. See protocol 19.2 Time Points of appendix D Correlative Studies
- I. Triglycerides Day 1 of cycles 3, 6, 9, 12 and then every 3 months until month 24. Then again at months 24, 30, & 36.
- J. Physical Exam during follow-up.
- K. Only if there is progression, as judged by the Investigator

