8. CRITERIA FOR RESPONSE, PROGRESSION, AND RELAPSE

For purposes of this study, patients should be restaged every 3 cycles during treatment (i.e., cycles 3, 6, 9, 12, etc.), then every 3 months for 1 year, then every 6 months for another year.

The Revised Response Criteria for Malignant Lymphoma is adopted.¹³

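### Table 1 schedules no serum IgM or M-protein, so the IgM limb of Waldenstrom progression cannot be applied and PFS in that subset is biased upward

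*Combined protocol and SAP*

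**What the plan says.** Section 3.1.1 admits "lymphoplasmacytic lymphoma/Waldenstrom disease (LPL/WM") alongside the other indolent histologies. It sets no minimum, cap or expected number.

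Section 8 adopts general lymphoma criteria, and 8.6 then gives Waldenstrom disease a separate table. In Table 4, CR requires a normal IgM level and a negative immunofixation. VGPR, PR, MR and SD are set by the percentage change in IgM from baseline. The IgM limb of progression is a 25% or greater "increase in serum IgM level* from lowest nadir (requires confirmation"), and the entry does not stop there: it reads "increase in serum IgM level* from lowest nadir (requires confirmation) and/or progression in clinical features attributable the disease". The footnote says how the change is to be measured: "Sequential changes in IgM levels may be determined either by M protein quantitation by densitometry or total serum IgM quantitation by nephelometry".

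The laboratory block of Table 1 is detailed. It runs from blood counts, creatinine, electrolytes and liver tests through "Uric Acid, Phosphate, LDH" to CMV PCR, thyroid function, triglycerides and viral serology. The nearest disease-related serum marker is "Beta2-Microglobulin", marked only before treatment and at end of treatment, and Table 4 does not use it. No row or footnote names IgM, M-protein, electrophoresis or immunofixation.

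On timing, section 8 says that "patients should be restaged every 3 cycles during treatment", with further restaging every 3 months for a year and every 6 months for another year.

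Section 14.4.1 runs PFS from ASCT to progression or death without saying which progression rule applies to Waldenstrom patients. Section 5.5 ties removal from study to section 8.4 alone.

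**The concern.** A progression rule based on change from nadir needs a series of measurements, and this one also needs a repeat to confirm the rise. If the calendar never asks for the measurement, that part of the rule exists only on paper. The resulting error is not random. A patient whose disease is returning only as rising IgM stays in the risk set as progression-free, so the Kaplan-Meier estimates at 1 and 2 years can only be too high on this account.

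The gap is also hard to repair after the fact. The research blood in Appendix D is optional and is collected for cell isolation; no serum or plasma bank is described from which a baseline could be measured later.

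**Working it through.** The plan states no figure on this point, so there is none to reproduce. The check compares the rule with the calendar and then gives a scale.

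**Rule against calendar**

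| What Table 4 needs for the IgM limb | What Table 1 and footnotes A to K schedule |
|---|---|
| Baseline IgM or M-protein | None |
| Serial values to establish the nadir | None on treatment, at restaging or in follow-up |
| A repeat value to confirm the rise | None |
| One comparable method over time | Not fixed; Table 4 allows two methods |

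IgM is mentioned nowhere outside section 8.6.

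**What the calendar can still detect**

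History, physical examination, performance status and blood counts are scheduled at cycle visits and in follow-up. Imaging is listed at restaging, but footnote D reads "CT, PET or PET/CT done PRN to follow measurable disease". Footnote G limits repeat marrow to confirming CR when the marrow was involved at baseline, or to suspected involvement. The clinical-features limb and death can therefore be observed. A patient whose only change is rising IgM triggers neither footnote.

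**Size per patient**

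Inputs: planned n = 34 (section 14); 1-year PFS of 60% at baseline and 80% expected (section 1.2.1); the number of LPL/WM patients is an assumption. Ignoring censoring, k missed events shift the estimate by k/34:

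| IgM-only progressions missed by the landmark | Upward shift in PFS |
|---|---|
| 0 | 0 |
| 1 | 1/34 = 2.9 points |
| 2 | 2/34 = 5.9 points |
| 3 | 3/34 = 8.8 points |
| 4 | 4/34 = 11.8 points |

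With the 31 patients also used in section 14, one missed event is 1/31 = 3.2 points.

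**A more realistic expectation**

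Assume 1 to 4 LPL/WM patients with the plan's own 1-year event rates, and suppose that every event is IgM-only and missed:

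- At 80% PFS, expected events are 0.20 × 1 = 0.2 to 0.20 × 4 = 0.8. The shift is 0.2/34 = 0.6 to 0.8/34 = 2.4 points.
- At 60% PFS, expected events are 0.4 to 1.6. The shift is 0.4/34 = 1.2 to 1.6/34 = 4.7 points.

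**Yardsticks**

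The 90% half-width at 80% PFS is about 1.645 × √(0.80 × 0.20/34) = 11.3 points. The efficacy aim is a gain of 80 − 60 = 20 points.

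**The case against.** The strongest reply is that progression in Table 4 has two limbs joined by and/or, and the second does not need IgM. A reader who stops at the IgM clause might infer that PFS in these patients cannot be assessed at all. The documents do not support that: clinical progression, imaging findings and death all remain PFS events that the calendar can capture.

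A reader might also infer that entry and removal depend on the missing test. They do not. Inclusion criterion 3 asks for no documented progression on clinical or imaging grounds. The synopsis exclusion for progressive disease and section 5.5 both point to 8.4, a nodal and imaging rule without IgM. Only the SD, PR or CR label in that inclusion criterion would touch IgM, and only if Table 4 were applied at entry.

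Third, multiplying an assumed 1 to 4 patients by 2.9 points might suggest that about 3 to 12 points of the PFS estimate are unassessable. That is an upper bound reached only if every such patient has an IgM-only progression that is missed by the landmark. Expected shifts are smaller, as shown above, and zero if no LPL/WM patient enrols.

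It is also fair to say that the primary endpoint is toxicity, that PFS is reported as an estimate with a 90% interval and no test, and that response rate is not a listed endpoint, so unassignable response categories affect no planned analysis. Sites may measure IgM in routine care, but the protocol neither requires it nor fixes a method.

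These replies limit the reach of the point. They do not supply the missing measurement.

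**Conclusion.** The point holds for the IgM limb only. Following the calendar exactly, that limb of Waldenstrom progression cannot be applied, and IgM-only progression would be missed or dated late. The error runs one way, towards higher 1- and 2-year PFS in the LPL/WM subset, while the rest of the rule still works.

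Each such event missed by the landmark is worth about 2.9 points. Under the assumed 1 to 4 patients the expected 1-year shift is at most about 0.6 to 4.7 points, inside the 11.3-point half-width. Late dating matters at a landmark only if it carries the event past that landmark.

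This rests on three assumptions: that at least one LPL/WM patient enrols, that sites do not measure IgM on their own initiative, and that 8.6 governs progression for PFS. The last is the natural reading of a separate Waldenstrom table, but 14.4.1 does not confirm it. If 8.4 alone were meant to define the endpoint, the progression row of Table 4 would have no role in PFS. Either way the text needs settling. It should be corrected, but it does not threaten the primary analysis.

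**What to change.** - Add one row to Table 1, for LPL/WM patients only: quantitative serum IgM or M-protein, by one method per patient, before treatment, at each restaging and at each follow-up visit.
- Add a repeat sample to confirm a rise of 25% or more. Immunofixation is needed only where CR is to be assigned.
- State in 14.4.1 which section defines a Waldenstrom progression event for PFS.
- Reconcile 5.5, which cites only 8.4, with 8.6.

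The calendar row alone would not be enough, because the PFS definition would still not say whether an IgM rise counts. Routine measurements use blood draws already scheduled at these visits, so the cost is a few extra laboratory tests in a small subset, plus an occasional confirmatory sample. The reported PFS may come out slightly lower, because events that would have been missed are counted.

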9. ADVERSE EVENTS: LIST AND REPORTING REQUIREMENTS

9.1 Adverse Event Definitions

CTCAE term (AE description) and grade: The descriptions and grading scales found in the revised NCI Common Terminology Criteria for Adverse Events (CTCAE) version 4.03 will be utilized for AE reporting. All appropriate treatment areas should have access to a copy of the CTCAE version 4.03. A copy of the CTCAE version 4.03 can be downloaded from the CTEP web site.

Attribution of the AE:

- Definite – The AE *is clearly related* to the study treatment.
- Probable – The AE *is likely related* to the study treatment.
- Possible – The AE *may be related* to the study treatment.
- Unlikely – The AE *is doubtfully related* to the study treatment.
- Unrelated – The AE *is clearly NOT related* to the study treatment.

The Definition of a Serious Adverse Event (SAE):

SAE is defined as any of the following:

- Any death that occurs while the patient is enrolled in the study or within 30 days of completing the study
- Immediately life-threatening adverse event
- Requires inpatient hospitalization
- Prolongation of an existing hospitalization
- Congenital anomaly/birth defect
- Medically important event
- Disability/incapacity (persistent or significant)

Progression of the cancer under study is not considered an adverse event, unless it results in hospitalization or death.

9.2 Adverse Events for Zydelig

The following is taken from the Investigator’s Brochure (IB) 6th Edition for Zydelig. Please note that this section will be replaced by the CAEPR for Zydelig when it becomes available.

9.2.1 Treatment-Emergent Hematological and Non-hematological Adverse Events in $\geq 5\%$ of All Subjects

Table 5

Adverse Reactions ($\geq 10\%$ of Subjects) in Patients with Indolent non-Hodgkin Lymphoma Treated with Zydelig 150 mg BID

Adverse Reaction	Zydelig Monotherapy N=146 (%)	
	Any Grade	Grade ≥ 3
Gastrointestinal disorders		
diarrhea ^(a)	68 (47)	20 (14)
nausea	42 (29)	2 (1)
abdominal pain ^(b)	38 (26)	3 (2)
vomiting	22 (15)	2 (1)
General disorders and administration site conditions		
fatigue	44 (30)	2 (1)
pyrexia	41 (28)	3 (2)
asthenia	17 (12)	3 (2)
peripheral edema	15 (10)	3 (2)
Infections and infestations		
upper respiratory tract infection	18 (12)	0
Respiratory, thoracic, and mediastinal disorders		
pneumonia ^(c)	37 (25)	23 (16)
cough	42 (29)	1 (1)
dyspnea	25 (17)	6 (4)
Skin and subcutaneous disorders		
rash ^(d)	31 (21)	4 (3)
night sweats	18 (12)	0
Nervous system disorders		
headache	16 (11)	1 (1)
Metabolism and nutrition disorders		
decreased appetite	24 (16)	1 (1)

Psychiatric disorders		
Insomnia	17 (12)	0

- (a) Diarrhea includes the following preferred terms: diarrhea, colitis, enterocolitis, and gastrointestinal inflammation.
- (b) Abdominal pain includes the following preferred terms: abdominal pain, abdominal pain upper, abdominal pain lower and abdominal discomfort.
- (c) Pneumonia includes the terms: pneumonia, pneumonitis, interstitial lung disease, lung infiltration, pneumonia aspiration, respiratory tract infection, atypical pneumonia, lung infection, pneumocystis jiroveci pneumonia, bronchopneumonia, pneumonia necrotizing, lower respiratory tract infection, pneumonia pneumococcal, pneumonia staphylococcal, pneumonia streptococcal, pneumonia cytomegaloviral, and respiratory syncytial virus infection.
- (d) Rash includes the following preferred terms: dermatitis exfoliative, rash, rash erythematous, rash macular, rash maculo-papular, rash pruritic, and exfoliative rash.

Treatment-emergent Laboratory Abnormalities in Patients with Indolent non-Hodgkin Lymphoma Treated with Zydelig 150 mg BID

Laboratory Abnormality	Zydelig Monotherapy N=146 (%)		
	Any Grade	Grade 3	Grade 4
Serum chemistry abnormalities			
ALT increased	73 (50)	20 (14)	7 (5)
AST increased	60 (41)	12 (8)	6 (4)
Hematology abnormalities			
neutrophils decreased	78 (53)	20 (14)	16 (11)
hemoglobin decreased	41 (28)	3 (2)	0
platelets decreased	38 (26)	4 (3)	5 (3)

Grades were obtained per CTCAE version 4.03.

Serious Adverse Events Reported as Possibly, Probably, or Definitely Related to Zydelig

Table 6

System Organ Class	Adverse Event
Blood and lymphatic system disorders	Anemia Febrile neutropenia Neutropenia Red cell aplasia Thrombocytopenia
Gastrointestinal disorders	Colitis Diarrhea Ischemic colitis Nausea Esophagitis Stomatitis Vomiting

General disorders and administration site conditions	Fatigue Fever Influenza-like symptoms Pyrexia
Hepatobiliary disorders	Cholecystitis Cholecystitis, acalculous Cholecystitis, acute
Infections and infestations	Abscess Brain abscess Cellulitis Cytomegalovirus infection Endocarditis Herpes zoster Herpes zoster, ophthalmic Meningitis Pneumonia Pneumonia fungal Pneumonia, Pneumocystis jiroveci Sepsis
Hepatotoxicity	ALT increased AST increased Hepatic enzyme increased Transaminase increased
Metabolism and nutrition disorders	Anorexia Fluid retention Hypercalcemia Tumor lysis syndrome
Renal and urinary disorders	Renal failure Renal failure, acute
Respiratory, thoracic, and mediastinal disorders	Atelectasis Hypoxia Pneumonia, organizing Pneumonitis Pulmonary embolism Pulmonary fibrosis
Skin and subcutaneous tissue disorders	Rash Rash, generalized Rash maculopapular

9.3 Adverse Event Characteristics/Evaluation

An investigator who is a qualified physician will evaluate all adverse events according to the NCI Common Terminology for Adverse Events (CTCAE), version 4.03. Any adverse event which changes CTCAE grade over the course of a given episode will have each change of grade recorded on the adverse event case report forms/worksheets.

All adverse events, regardless of CTCAE grade must also be evaluated for seriousness.

- CTCAE term (AE description) and grade: The descriptions and grading scales found in the revised NCI Common Terminology Criteria for Adverse Events (CTCAE) version 4.03 will be utilized for AE reporting. All appropriate treatment areas should have access to a copy of the CTCAE version 4.03. A copy of the CTCAE version 4.03 can be downloaded from the CTEP web site (http://ctep.cancer.gov/protocolDevelopment/electronic_applications/ctc.htm).

Table 7

V4.0 CTCAE Grading	Grade 1	Mild; asymptomatic or mild symptoms; clinical or diagnostic observations only; intervention not indicated.
	Grade 2	Moderate; minimal, local or noninvasive intervention indicated; limiting age-appropriate instrumental ADL.
	Grade 3	Severe or Medically Significant but not immediately life-threatening; hospitalization or prolongation or hospitalization indicated; disabling; limiting self-care ADL.
	Grade 4	Life Threatening consequences; urgent intervention indicated.
	Grade 5	Death related to AE
Seriousness	A serious adverse event is any adverse event occurring at any dose or during any use of the investigational condition that:	
	†Results in death; or	
	†Is life threatening; or places the subject, in the view of the investigator, at immediate risk of death from the event as it occurred (Note: This does not include an adverse event that, had it occurred in a more severe form, might have caused death.); or	
	†Results in a persistent or significant disability/incapacity (substantial disruption of one’s ability to conduct normal life functions); or	
	†Results in or prolongs an existing inpatient hospitalization (hospitalization is defined as an inpatient admission, regardless of length of stay, even if the hospitalization is a precautionary measure for continued observation. (Note: Hospitalization [including hospitalization for an elective procedure] for a preexisting condition which has not worsened does not constitute a serious adverse event.); or	
	†Is a congenital anomaly/birth defect (in offspring of subject exposed to the investigational condition regardless of time to diagnosis);or	
	Other important medical events that may not result in death, not be life threatening, or not require hospitalization may be considered a serious adverse event when, based upon appropriate medical judgment, the event may jeopardize the subject and may require medical or surgical intervention to prevent one of the outcomes listed previously (designated above by a †).	
Duration	Record the start and stop dates of the adverse event. If less than 1 day, indicate the appropriate length of time and units.	
Action Taken	Did the adverse event cause the study treatment to be discontinued?	
Relationship to Test Condition	Did the investigational condition cause the adverse event? The determination of the likelihood that the investigational condition caused the adverse event will be provided by an investigator who is a qualified physician. The investigator’s signed/dated initials on the source document or worksheet that supports the causality noted on the AE form, ensures that a medically qualified assessment of causality was done. This initialed document must be retained for the required regulatory time frame. The criteria below are intended as reference guidelines to assist the investigator in assessing the likelihood of a relationship between the test drug and the adverse event based upon the available information. The following components are to be used to assess the relationship between the investigational condition and the AE; the greater the correlation with the components and their respective elements (in number and/or intensity), the more likely the investigational condition caused the adverse event (AE):	
	Exposure	Is there evidence that the subject was actually exposed to the investigational condition such as: reliable history, acceptable compliance assessment (pill count, diary, etc.), expected pharmacologic effect, or measurement of drug/metabolite in bodily specimen?
	Time	Did the AE follow in a reasonable temporal sequence from administration of the

Course	investigational condition? Is the time of onset of the AE compatible with a study-induced effect (applies to trials with investigational medicinal product[s])?
Likely Cause	Is the AE not reasonably explained by another etiology such as underlying disease, other drug(s)/vaccine(s), or other host or environmental factors?

• ‘Expectedness’: AEs can be ‘Unexpected’ or ‘Expected’ for expedited reporting purposes only. The following abnormalities/adverse events are considered "expected" and their presence/absence should be solicited, and severity graded, at baseline and for each cycle of treatment.

- ✓ Fatigue
- ✓ Skin rash
- ✓ Diarrhea
- ✓ Decreased neutrophils, hemoglobin and platelet count
- ✓ Increased serum ALT and AST
- ✓ Cough and pneumonitis
- ✓ Fever
- ✓ Infection

